investigator. The investigator will retain accountability for participant's oversight and all medical decisions (i.e. protocol specified medical procedures, AE/SAE assessment and reporting, changes in medication, etc.).

As per [Section 4.6](#), during a Public Health emergency as declared by Local or Regional authorities i.e. pandemic, epidemic or natural disaster or in special circumstances, that limits or prevents on-site study visits, alternative methods of providing continuing care may be implemented by the investigator as the situation dictates. If allowed by local Health Authority and depending on operational capabilities, phone calls, virtual contacts (e.g. tele consult) or visits by site staff/home nursing staff to the participant's home can replace on-site study visits, for the duration of the disruption until it is safe for the participant to visit the site again. For more details refer to [Section 8.6](#).

Participants who prematurely discontinue iptacopan treatment for any reason during the Core treatment period should continue in the study up to Week 24 visit, completing all scheduled visits assessments. Please, refer to [Section 9.1.1](#) for details on the recommended procedures to follow in case of permanent discontinuation.

Participants who prematurely discontinue iptacopan treatment during the Extension treatment period of the study for any reason, and if possible, should continue in the study up to the Week 48 visit completing all scheduled visit assessments. The same guidance for managing iptacopan permanent discontinuation as in the Core treatment period applies ([Section 9.1.1](#)).

At this final visit, all dispensed investigational product should be reconciled, and the adverse event and concomitant medications should be recorded on the CRF.

Table 8-1 Assessment schedule – Core treatment period

Period	Screening		Core treatment period											
	Visit Name	Hb /LDH confirm.	Day 1	Day 7	Day 14	Day 28	Day 42	Day 56	Day 84	Day 112	Day 126	Day 140	Day 154	Day 168 ⁷
Visit Numbers	1	1	101	102	103	104	105	106	107	108	109	110	111	112
Days	-56 to -1	-56 to -1	1	7 ±1	14 ±1	28 ±1	42 ±3	56 ±3	84 ±3	112 ±3	126 ±3	140 ±3	154 ±3	168 ±3
Weeks	-8 to -1	-8 to -1	1	1	2	4	6	8	12	16	18	20	22	24
Informed consent	X													S
Eligibility criteria	X	X												
Demography	X													
Medical history/current medical conditions	X													
Vaccination ¹	X													
Alcohol and Smoking history	X													

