² Local reticulocytes testing can be performed at the same time as the central testing during the Screening period. In the event that the absolute reticulocytes count as assessed by the central laboratory during the Screening period is below the protocol defined threshold (absolute reticulocytes <100x10⁹/L) and only in this scenario, the results from the local lab testing can be used to determine participant's eligibility.

³ PK samples will be taken pre-dose and approximately 2h post-dose.

⁴ If the DNA sample is not taken at Day 1 visit, it can be taken at any visit thereafter.

⁵ First PRO completion should occur at a screening visit prior to Day 1 and before any other assessment at that visit.

⁶ Only FACIT-Fatigue [REDACTED] will be carried out on Day 7.

⁷ For participants not agreeing to continue in the Extension treatment period after completing Day 168 visit, End of Study will be after completing recommended procedures defined in [Section 9.1.1](#), for participants prematurely discontinuing study treatment before Day 168 but remaining in the study for abbreviated visits, please refer to [Section 9.1.1](#) for the close monitoring and additional assessments/visits to be performed in between abbreviated visits.

[REDACTED]

Table 8-2 Assessment Schedule - Extension treatment period

Period	Extension treatment Period					
	Day 196	Day 224	Day 252	Day 280	Day 308	Day336/EOS
Visit Name	201	202	203	204	205	9999 ¹
Visit Numbers	201	202	203	204	205	9999 ¹
Days	196 ± 5	224 ± 5	252 ± 5	280 ± 5	308 ± 5	336 ± 5
Weeks	28	32	36	40	44	48
Blood pressure and pulse rate	X	X	X	X	X	X
Physical examination						S
Body weight						X
Body temperature	X	X	X	X	X	X
Pregnancy test(urine)						S
Clinical Chemistry (full)		X				X
Clinical Chemistry (abbreviated)	X		X	X	X	
Hematology (full)	X	X	X	X	X	X
Coagulation/markers of thrombosis	X	X	X	X	X	X
Panel of hormones blood samples	X	X		X		X
 						
Urinalysis	X	X	X	X	X	X
Urine Albumin/Creatinine ratio			X			X
Breakthrough hemolysis				X		
MAVE				X		
 						
RBC transfusion				X		
12-lead Electrocardiogram (ECG)						X
Adverse Events				X		
Concomitant medications				X		
 						
Surgical and medical procedures				X		
Patient reported outcomes	X	X	X	X	X	X

Period	Extension treatment Period					
	Day 196	Day 224	Day 252	Day 280	Day 308	Day336/EOS
Visit Name	201	202	203	204	205	9999 ¹
Visit Numbers	201	202	203	204	205	9999 ¹
Days	196 ± 5	224 ± 5	252 ± 5	280 ± 5	308 ± 5	336 ± 5
Weeks	28	32	36	40	44	48
Iptacopan DAR				X		

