8.3.4 Patient Reported Outcomes (PRO) - FACIT-Fatigue

The FACIT-Fatigue is a 13-item questionnaire that assesses self-reported fatigue and its impact upon daily activities and function. It will be used to assess patient-reported fatigue. FACIT-Fatigue is one of many different FACIT scales part of a collection of health-related quality of life (HRQoL) questionnaires referred to as the FACIT Measurement System (Yellen et al 1997, Webster et al 2003). The use of the FACIT-F in PNH patients has been reported in several publications and is sensitive to changes in disease status, allowing demonstration of statistically significant and clinically meaningful results (Brodsky et al 2008, Ueda et al 2018, Kulasekararaj et al 2019). All FACIT scales are scored so that a high score is better. As each of the 13 items of the FACIT-F Scale ranges from 0-4, the range of possible scores is 0-52, with 0 being the worst possible score and 52 the best. For additional Patient Reported Outcomes (PROs) assessed in the study, please refer to [Section 8.5.1](#).

The PROs will be completed by participants on an electronic PRO (ePRO) device, first PRO completion should occur at a screening visit prior to Day 1. The PROs will be completed before any other procedure or assessment at the screening and Day 1 visits. The questionnaires should be completed in the language with which the respondent is most familiar. The participant should be given sufficient space and time to complete the questions. The participant should be made aware that completed questionnaires are not reviewed by the investigator/ study personnel.

Following the Day 1 visit, the participant will take home the ePRO device to be able to complete the PROs at home prior to visits to the clinic site. Detailed instructions describing administrative procedures of the PROs including participant completion via ePRO will be provided to the sites.

If a participant is not able to self-administer the ePRO (e.g. due to illiteracy or blindness) or refuses to complete the questionnaires, this should be documented in the source documents. A participant's inability or refusal to complete a questionnaire(s) is not a protocol deviation.

Detailed instructions describing administrative procedures of the PROs including participant completion via ePRO will be provided to the sites.

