Participants who permanently discontinue study medication during the Extension treatment period, and if possible, should complete the visits as scheduled up to Week 48.

If the participant cannot or is unwilling to attend any visit(s), the site staff should maintain regular telephone contact with the participant, or with a person pre-designated by the participant. This telephone contact should preferably be done according to the study visit schedule.

After study treatment discontinuation, at a minimum, in abbreviated visits, the following data should be collected at clinic visits or via telephone/email contact:

- New / concomitant treatments
- Safety laboratory assessments
- Adverse Events / Serious Adverse Events

All dose changes must be recorded on the appropriate CRF. The investigator must also contact the IRT to register the participant's discontinuation from study treatment.

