1.2.1 Primary estimands

The primary clinical question of interest is:

What is the effect of iptacopan, regardless of discontinuations of study drug or occurrence of Breakthrough hemolysis (BTH) or Major Adverse Vascular Events (MAVEs) on the primary endpoint (a composite of improvement in hemoglobin levels and absence of RBC transfusions), as assessed by the proportion of responders?

This primary estimand captures both the hematological effect of the study drug (as evaluated by a clinically relevant increase of ≥ 2 g/dL in hemoglobin levels) and the absence of RBC transfusions after Day 14 which are regarded as treatment failure.

The attributes of the primary estimand are:

- Population: PNH Patients ≥ 18 years old with hemolysis (LDH > 1.5 ULN) and anemia (hemoglobin < 10 g/dL), and who have not received any complement inhibitor therapy (including anti-C5 antibody).
- Treatment of interest: the investigational treatment iptacopan at a dose of 200 mg b.i.d regardless of whether the patient discontinues treatment (treatment policy).
- Intercurrent events: Transfusions (after Day 14) will be considered treatment failures and as such captured in the endpoint. Discontinuations of study medication for any reason, BTH events, and MAVEs will be handled with a treatment policy strategy.
- The summary measure: the probability of being a responder, standardized to the population of patients assigned to iptacopan in this study.

The justification of handling of intercurrent events is in [Table 1-3](#). The overview of estimands and estimation methods is in [Table 5-1](#) in [Section 5.2](#).

Table 1-3 Justification of handling of intercurrent events

Intercurrent event	Handling strategy	Justification
Discontinuation of study medication	Treatment policy	The effect of treatment will be assessed even when participants discontinue study medication. Data collection will be maintained and available measurements post-treatment discontinuation used maintaining the treatment label as assigned at enrollment.
Breakthrough hemolysis events	Treatment policy	The effect of treatment will be assessed. Breakthrough hemolysis may affect the endpoints considered in the study, hence data collection will be maintained and available measurements collected after breakthrough hemolysis event keeping the treatment label as assigned at enrollment.

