2.6.1.8 Rates of clinical breakthrough hemolysis

Information of clinical breakthrough events as collected on the 'Breakthrough Hemolysis' CRF page will be used for analysis and the information will also be reported as a part of the adverse event summaries. The number and percentage of patients experiencing treatment emergent clinical breakthrough hemolysis events in the core treatment and extension treatment periods will be summarized. The information on whether the patient received packed-RBC transfusions and the quantity of packed-RBC transfusions due to clinical breakthrough hemolysis will be summarized. Clinical breakthrough hemolysis events (including those in the screening period) will be listed and the treatment emergent events will be flagged.

Based on FAS, the estimation of rates of clinical breakthrough hemolysis will be carried out using a negative binomial model. The model will include the following covariates: transfusion dependence, age (indicator of age ≥ 45 years), sex, indicator variable of baseline hemoglobin ≥ 8 g/dL. Following the treatment policy strategy for handling treatment discontinuations, the offset variable will be defined as the time from Day 1 till minimum (end of study, end of core treatment period).

If the above model fails to converge due to low frequency of occurrences, then the model will be run considering no covariates in the negative binomial model. If the model fails to converge, then a Poisson model without covariates will be fitted. If both negative binomial and Poisson model fail to converge, the Wilson ([Miettinen and Nurminen, 1985](#)) method will be implemented.

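### The minimum data set after stopping iptacopan has no route for FACIT-Fatigue and does not name the transfusion, BTH and MAVE pages that the analyses read

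*Protocol*

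**What the plan says.** **Default follow-up.** Protocol Section 8 says that participants who stop iptacopan early in the Core period "should continue in the study up to Week 24 visit, completing all scheduled visits assessments". Sections 6.1.4 and 9.1.1 say the same in substance.

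**Abbreviated follow-up.** Table 8-1 footnote 7 provides "for participants prematurely discontinuing study treatment before Day 168 but remaining in the study for abbreviated visits" and refers to Section 9.1.1. There the floor is introduced with "After study treatment discontinuation, at a minimum, in abbreviated visits, the following data should be collected at clinic visits or via telephone/email contact". It has three items: "New / concomitant treatments", "Safety laboratory assessments", and adverse events, serious or not.

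**What the analysis expects.** The estimands handle discontinuation by treatment policy. SAP Table 1-3 states: "Data collection will be maintained and available measurements post-treatment discontinuation used maintaining the treatment label as assigned at enrollment". SAP 2.5.1 takes transfusions from a dedicated CRF page, and SAP 2.6.1.7 and 2.6.1.8 take MAVEs and BTH from theirs. FACIT-Fatigue comes from the ePRO device. Protocol 8.3.4 says that after Day 1 "the participant will take home the ePRO device to be able to complete the PROs at home".

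**Rate denominator.** For BTH, and in the same terms for MAVEs, "the offset variable will be defined as the time from Day 1 till minimum (end of study, end of core treatment period".

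**Missing scores.** SAP 2.6.2 replaces secondary-endpoint values that are missing after study withdrawal or iptacopan discontinuation with draws from a normal distribution. Its mean and standard deviation come from all baseline values.

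**The concern.** A treatment-policy analysis needs outcomes observed after the drug is stopped. The protocol states a full default and a reduced floor, and gives no rule for moving from one to the other. The floor is written for clinic visits as well as telephone or email contact, so it is not confined to people who cannot attend. A site that follows it exactly meets Section 9.1.1 and still collects no FACIT-Fatigue, although the participant may have the device at home.

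The transfusion, BTH and MAVE pages raise a lesser worry. The list does not mention them, yet the SAP analyses read them. An off-drug event entered only as an adverse event or concomitant treatment would not be in the source that the SAP names. The period matters because Protocol 4.5 identifies hemolysis after stopping a complement inhibitor as a risk, and Section 9.1.1 asks for close monitoring for it.

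**Working it through.** **1. Is each outcome reachable from the minimum list?**

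| Outcome | Route through a listed item | Source read by the SAP |
|---|---|---|
| RBC transfusion | Concomitant treatments: Protocol 6.2.1 includes blood transfusions; 8.3.2 requires hemoglobin, units and symptoms on the CRF | Transfusion page |
| BTH | Adverse events: 8.3.3 requires the BTH page as well as the AE page | BTH page |
| MAVE | Adverse events: 8.3.6 requires the dedicated page as well as the AE page | MAVE page |
| FACIT-Fatigue | None | ePRO device |

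Under Protocol 10.1.1, adverse events after discontinuation are collected until 7 days after the last dose or end of study, whichever is later. The first three outcomes are therefore reachable, but only by reading other sections together with 9.1.1. The fourth is not.

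**2. What a remote contact cannot give.** The responder and transfusion-avoidance endpoints also fail a participant who met the transfusion criteria without being transfused. Judging that needs hemoglobin and, in the higher band, symptoms. Clinical BTH needs LDH. Safety laboratory tests plausibly supply hemoglobin and LDH at an in-person visit. A telephone call does not.

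**3. Plan's own figures.** The stated half-width reproduces: 1.96 × √(0.25/40) = 0.155. It does not depend on this point. The documents give no discontinuation rate, BTH or MAVE rate, or person-time.

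**4. Person-time.** Planned Core person-time is 40 × 168 / 365.25 = 18.40 years. Suppose, as an assumption, that 1 to 8 of 40 stop at Day 84:
- off-drug time is 1 × 84/365.25 = 0.23 years to 8 × 84/365.25 = 1.84 years, which is 1.25% to 10% of the total;
- if the stopping day varies from 126 to 42, the share runs from 0.6% (1 participant, Day 126) to 15% (8 participants, Day 42).

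The denominator alone matters little. With 2 on-drug events and 4 stopping at Day 84, the rate is 2/18.40 = 0.109 per year over all time and 2/17.48 = 0.114 over on-drug time.

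**5. One missed event.** 1/18.40 = 0.054 per year. For example, 2 events read where 3 occurred gives 0.109 instead of 0.163 per year.

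**6. One misclassified participant.** 1/40 = 2.5 percentage points on transfusion avoidance.

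**7. FACIT-Fatigue.** Treat the mean change as a simple average and the imputed change as zero on average. A participant whose true off-drug change is d points then shifts the mean by d/40. Taking d = 5, the responder cut-off in Protocol 12.5.4, as an illustration: 5/40 = 0.125 points each.

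**8. Does off-drug time enter the offset?** SAP 1.1 ends the Core period with the Week 24 assessments, and 2.1.1.5 with the Day 168 visit (or end of study for those who leave earlier). SAP 2.4.1 ends it at the last administration. The first two put off-drug time in the offset; the third takes it out.

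**The case against.** The strongest reply is that the list is only a floor. Full visits to Week 24 are the stated plan, and the list follows a paragraph on telephone contact with participants who cannot or will not attend. An event left off its dedicated page would breach Protocol 8.3.2, 8.3.3 or 8.3.6; the list does not permit it. This largely stands. A reader might infer that transfusions, BTH and MAVEs are dropped from collection after discontinuation, or that the hemoglobin and symptoms behind a transfusion go unrecorded. The documents do not support either inference.

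A second reply is that missing data are handled. FACIT-Fatigue has a stated imputation. For transfusion avoidance, SAP 2.5.3 counts imputed hemoglobin at or below 9 g/dL (8 g/dL for Chinese participants) as needing transfusion, which pushes toward failure wherever it applies. This stands in part, so transfusion avoidance cannot be said to be biased upward. But the return-to-baseline hemoglobin rule in 2.5.3 is written for study withdrawal, and a participant who stays in by telephone has not clearly withdrawn. For FACIT-Fatigue, a draw from baseline is a substitute for the off-drug score. It is least apt for someone moved to replacement therapy, which Section 9.1.1 foresees.

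A third reply is that the BTH and MAVE rates carry no success threshold; the 15% criterion applies to the primary endpoint. That stands and limits the consequence.

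**Conclusion.** The point holds in a limited form. The protocol does not say when abbreviated visits may replace full ones. A participant followed exactly to the minimum list yields no FACIT-Fatigue, so imputation stands in for a value that the treatment-policy estimand wants observed. For transfusions, BTH and MAVEs the defect is a missing cross-reference: a missed event is possible, not certain. The sizes are per occurrence: 0.054 per year for a missed BTH or MAVE (with the full 18.40 planned person-years as denominator) and 2.5 points for a misclassified participant.

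A reader might go further and compute a bias in the BTH rate. Assume 2 to 4 of 40 stop at Day 84, with 0.1 BTH per year on drug, 1 to 2 per year off drug, and every off-drug event lost:
- low end: 0.46 / (17.94 × 0.1 + 0.46 × 1) = 0.46/2.254 = 20%;
- high end: 1.84 / (17.48 × 0.1 + 0.92 × 2) = 1.84/3.588 = 51%.

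The arithmetic is right, but the documents fix none of these inputs and the total loss is a worst case. If a quarter of the events were lost, also an assumption, the figures would be about 5% to 13%. No overall bias can be stated. Nor can it be taken as settled that off-drug person-time is counted. The treatment-policy wording and the Week 24 definition say so, but SAP 2.4.1 says otherwise.

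**What to change.** - **Protocol 9.1.1:** for the Core period, add to the minimum list FACIT-Fatigue on the home ePRO device and completion of the Transfusion, BTH and MAVE CRF pages.
- **Protocol 9.1.1 and Table 8-1 footnote 7:** state that the full Table 8-1 schedule applies to Week 24, and that abbreviated visits apply only when a participant cannot or will not attend full visits. Align the footnote with Section 8.
- **SAP 1.1, 2.1.1.5 and 2.4.1:** reconcile the end of the Core period so that the BTH and MAVE offset uses one definition. Week 24/Day 168 is the one consistent with treatment policy.

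The pages and the device already exist. The cost is a few more questions per contact for what may be a handful of discontinuers, plus a protocol amendment with the approvals that Protocol 14.1 requires and a short SAP edit.

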9.1.2 Withdrawal of informed consent

Participants may voluntarily withdraw consent to participate in the study for any reason at any time. Withdrawal of consent occurs only when a participant:

- Does not want to participate in the study anymore,

and

- Does not want any further visits or assessments

and

- Does not want any further study related contacts

In this situation, the investigator should make a reasonable effort (e.g. telephone, e-mail, letter) to understand the primary reason for the participant's decision to withdraw his/her consent and record this information.

Where consent to the use of personal and coded data is not required, participant therefore cannot withdraw consent. They still retain the right to object to the further use of personal data.

Study treatment must be discontinued and no further assessments conducted, and the data that would have been collected at subsequent visits will be considered missing.

Further attempts to contact the participant are not allowed unless safety findings require communicating or follow-up.

All efforts should be made to complete the assessments prior to study discontinuation. A final evaluation at the time of the participant's study discontinuation should be made as detailed in the assessment table.

Novartis will continue to retain and use all research results (data) that have already been collected for the study evaluation.

9.1.3 Lost to follow-up

For participants whose status is unclear because they fail to appear for study visits without stating an intention to discontinue or withdraw, the investigator must show "due diligence" by documenting in the source documents steps taken to contact the participant, e.g. dates of telephone calls, registered letters, etc. A participant should not be considered as lost to follow-up until due diligence has been completed or until the end of the study.

9.1.4 Early study termination by the sponsor

The study can be terminated by Novartis at any time.

Reasons for early termination:

- Unexpected, significant, or unacceptable safety risk to participants enrolled in the study
- Decision based on recommendations from applicable board(s) after review of safety and efficacy data

- Discontinuation of study drug development

In taking the decision to terminate, Novartis will always consider participant welfare and safety. Should early termination be necessary, participants must be seen as soon as possible (for an EOS visit) and treated as a prematurely withdrawn participant. The investigator may be informed of additional procedures to be followed in order to ensure that adequate consideration is given to the protection of the participant's interests. The investigator or sponsor depending on local regulation will be responsible for informing IRBs/IECs of the early termination of the trial.

